14.3. Analysis Populations

Safety Population:

All subjects who were administered any test article excluding subjects who drop out prior to administering any test article. At least one observation should be recorded.

Per-Protocol Population:

All subjects who have successfully completed all visits and did not substantially deviate from the protocol as determined by the trial cohort review committee prior to database hard lock (Per-Protocol Population). Justification of excluding subjects with protocol deviations in the Per-Protocol Population set will be documented in a memo to file.

Intent-to-Treat (ITT) Population:

All subjects regardless of actual treatment and subsequent withdrawal from study or deviation from protocol. At least one observation should be recorded.

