4. STUDY DESIGN AND RATIONALE

4.1. Description of Study Design

The clinical study is a single-ARM, single-masked, clinical trial. The mask will be a partial mask in that the lenses will be over-labeled and the specific brand of the contact lens will not be disclosed to the subject however the subject will be aware of the photochromic properties of the contact lens. There is one study treatment with two wearing cycles. A total of approximately 80 eligible subjects will be targeted to complete the study. The test article in the first wearing cycle will be dispensed for 12 ± 2 days and at the follow-up the final lens measurements will occur. Subjects will complete a 7 ± 3 days washout and then return for the second wearing cycle. New lenses with same power of the final pair from Visit 1 will be dispensed and the above sequence repeated. The lens in the second wearing cycle will not be optimized.

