5. TEST ARTICLE ALLOCATION AND MASKING

5.1. Test Article Allocation

The study lenses will be worn in a bilateral fashion using a single-arm design with 1 lens type and 2 wearing cycles.

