5.2. Masking

This is a single-masked study with the subjects being masked. The lenses from different wearing cycles will be over-labeled using different letters so that the subjects don't know for sure the lenses are identical.

Under normal circumstances, the mask should not be broken until all subjects have completed the study and the database is finalized. Otherwise, the mask should be broken only if specific emergency treatment/course of action would be dictated by knowing the treatment status of the subject. In such cases, the Investigator may, in an emergency, contact the medical monitor. In the event the mask is broken, the Sponsor must be informed as soon as possible. The date, time, and reason for the unmasking must be documented in the subject record. The Investigator is also advised not to reveal the study treatment assignment to the clinical site or Sponsor personnel.

Subjects who have had their treatment assignment unmasked are expected to return for all remaining scheduled evaluations. Subjects who are discontinued may be replaced.

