14. STATISTICAL METHODS

14.1. General Considerations

All data summaries and statistical analyses will be performed using the Statistical Analysis System (SAS) software Version 9.4 (SAS Institute, Cary, NC). Throughout the analysis of data, the results for each subject/eye will be used when available for summarization and statistical analysis. Unscheduled visits will be summarized separately and will be excluded from the statistical analysis.

Summary tables (Descriptive statistics and/or frequency tables) will be provided for all baseline variables, efficacy variables and safety variables as appropriate. Continuous variables will be summarized with descriptive statistics (n, mean, standard deviation [SD], median, minimum and maximum). Frequency count and percentage of subjects or eyes within each category will be provided for categorical data.

Summaries will be presented by study lens type and will be performed separately by completion status (Safety Population or Per-Protocol Population). All analyses will be conducted on per-protocol population (see Section 14.3).

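### Every hypothesis test uses a per-protocol set fixed by unlisted committee judgement and by completion of all visits; in a single-arm trial, pre-lock review without stated masking to scores only partly guards that set

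*Combined protocol and SAP*

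**What the plan says.** Section 14.3 gives the per-protocol set two conditions: successful completion of all visits, and that the subject "did not substantially deviate from the protocol as determined by the trial cohort review committee prior to database hard lock". For exclusions it adds: "Justification of excluding subjects with protocol deviations in the Per-Protocol Population set will be documented in a memo to file". Section 14.1 then states: "All analyses will be conducted on per-protocol population".

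The design is a "single-arm design with 1 lens type and 2 wearing cycles" (Section 5.1). On masking, Section 5.2 says: "This is a single-masked study with the subjects being masked". No masking of the committee to acuity or CLUE scores is described. Section 14.5 compares a single-group mean with a fixed value: upper 95% limit below +0.10 logMAR (distance) or +0.17 logMAR (intermediate and near), and lower 95% limit above 32 CLUE points.

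Section 14.3 also defines an ITT set, "All subjects regardless of actual treatment and subsequent withdrawal from study or deviation from protocol", but no analysis is assigned to it. The only sensitivity analysis, in Section 14.9, is multiple imputation if dropout exceeds 15%. Under Section 7.2, step 3.11, a subject whose vision is unacceptable at Visit 3 is discontinued.

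**The concern.** In a masked randomised trial, settling the analysis set before lock works because reviewers cannot tell which arm an exclusion favours. Here there is no arm to conceal. Every score belongs to the test lens, so anyone who sees a score knows which way removing it moves the result. The term that governs exclusion is undefined, and the memo records a choice without limiting it.

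At stake is the 2.5% false-pass rate that each two-sided 95% interval is meant to give in the success direction. If exclusion is related to score, even loosely, that rate is not held, and no planned model-based analysis would show it.

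A second route needs no assumption about the committee. Requiring completion of all visits removes subjects who leave because of poor vision, together with scores they had already given.

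**Working it through.** **Inputs.** N = 80, SD 17 (CLUE) and 0.12 (acuity), two-sided alpha 0.05, assumed true means 38 to 42 (CLUE), 0.00 to 0.05 (distance) and 0.08 to 0.12 (intermediate and near), all from Section 14.2. Thresholds are from Section 14.5. Section 2.3 gives +0.01 logMAR for distance, but the distance table in Section 14.2 reproduces only with 0.10, so 0.10 is used. The numbers of deviators and exclusions are not in the documents and are assumed.

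**1. The plan's own figures.** One-sample t-test with noncentrality (difference × √n)/SD. For CLUE at 38: 6 × √87 / 17 = 3.29, power 0.902. All nine sample sizes (18, 26, 63; 21, 33, 63; 87, 50, 33) and their powers reproduce.

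**2. Precision at N = 80.** Half-width = 1.990 × SD/√80, which is 3.78 CLUE points or 0.027 logMAR.

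**3. Upper bound: remove the worst k of all 80.** 200,000 simulated normal samples with the true mean on the threshold; the 95% t-interval is recomputed on the remaining 80 − k.

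| k removed | shift in mean (SE) | false-pass rate |
|---|---|---|
| 0 | 0 | 2.5% |
| 1 | 0.28 | 5.1% |
| 2 | 0.52 | 8.6% |
| 4 | 0.95 | 18.8% |

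One SE is 17/√80 = 1.90 CLUE points or 0.12/√80 = 0.0134 logMAR, so k = 4 shifts the mean by about 1.8 points or 0.013 logMAR.

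**4. Exclusion limited to deviators.** Suppose d subjects deviate, unrelated to score, and the worst k of those d are removed.

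| d | k = 1 | k = 2 | k = 4 |
|---|---|---|---|
| 4 | 3.2% | 3.4% | 2.5% |
| 8 | 3.7% | 4.5% | 5.0% |
| 16 | 4.1% | 5.6% | 8.2% |

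With d = k = 4 there is no choice left, so the rate returns to 2.5%. If instead five of all 80 are removed on a proxy correlated 0.5 with the score, the rate is 8.7%; at correlation 0 it stays at 2.5%.

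**5. Where it can change a result.** Take an evenly spread normal sample with CLUE mean 35.0: the lower limit is 31.2 (fail), and removing the two lowest gives about 32.4 (pass). For near acuity with mean 0.150, the upper limit is 0.177 (fail), and removing the two worst gives about 0.168 (pass). At the planning values with N = 80, power is at least 0.957 for acuity, 0.986 at CLUE 40 and 0.877 at CLUE 38, for which the plan's own table asks for 87 subjects.

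**6. The completion rule.** Step 3.11 discontinues a subject for unacceptable vision at Visit 3. That subject has not completed all visits, so Section 14.3 keeps them out of the per-protocol set. Section 14.1 then drops their Visit 2 acuity and CLUE scores from the primary tests. The size depends on how many such subjects there are, which the documents do not give.

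A simple t-interval stands in for the planned mixed model, which adjusts CLUE for baseline and uses both time points.

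**The case against.** A reader might infer that the committee will see scores and can drop poor performers at will, or that review before lock gives no protection. The documents support neither. They are silent on what the committee sees. A decision fixed before hard lock, with a recorded reason, prevents re-selection after the final analysis. Only subjects with a deviation can be excluded on this ground, and Section 10 requires deviations to be notified to the sponsor and tracked, with major ones reported within 24 hours of discovery. For that reason the 19% figure is a ceiling: it needs all four of the poorest scorers to be deviators.

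Section 14.1 also plans summaries separately for the Safety and Per-Protocol Populations, with efficacy variables included as appropriate. A marked difference might therefore show descriptively.

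All of this stands and reduces the size of the problem. It does not remove it. Tracking deviations does not say which of them exclude, and Section 10 does not define a major deviation or link it to the per-protocol set. Descriptive Safety summaries do not give the model-based interval on which the conclusion rests. The imputation in Section 14.9 is triggered by dropout alone and does not address deviation exclusions. The completion rule is unaffected by any of these arguments.

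**Conclusion.** The point holds as a gap in safeguards. It is not evidence that the analysis set will be shaped by the results. The plan permits score-aware exclusion without stating that it occurs, and no planned model-based analysis would reveal its effect.

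For each test, with the true mean on the threshold, the false-pass rate moves from 2.5% to about 2.5% to 8% under the assumed range of 4 to 16 score-unrelated deviators with 1 to 4 excluded. It reaches about 5%, 9% or 19% at the upper bound for 1, 2 or 4 removed. Exclusions unrelated to score cause no inflation.

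The effect matters only for results close to a threshold. At the planned acuity values and at CLUE 40 or above, a few exclusions would rarely change the conclusion. CLUE with a true mean near 38 is the most exposed.

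The loss of Visit 2 scores for subjects discontinued at Visit 3 follows directly from the text and tends to favour the lens, by an amount that cannot be computed from the documents.

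**What to change.** - **Section 14.3, committee review.** State that the committee decides from listings with acuity, CLUE, MRD and subjective-acceptance data removed.
- **Section 14.3, excluding deviations.** Replace open judgement with a closed list taken from rules already in the protocol: eligibility breach, visit outside its window, Visit 3 lens power different from that dispensed at Visit 1, and wear below the stated daily minimum. Fix it before any Visit 2 data are reviewed. Low wear may itself follow from poor vision, which is a further reason for the next change.
- **Sections 14.1 and 14.5, supporting estimate.** Report each primary model estimate and interval also for all dispensed subjects with Visit 2 or Visit 4 data, using the ITT set already defined. Include both deviation-excluded subjects and non-completers, so that Visit 2 scores of subjects discontinued at Visit 3 are counted.

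The cost is a few sentences of text, one redacted listing and one extra run per primary model. No new data are needed and no clinical rule changes.

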14.4. Level of Statistical Significance

All planned analysis for this study will be conducted with an overall type I error rate of 5%.

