2.3. Hypotheses

The following primary hypotheses will be tested throughout this investigation.

Primary Hypotheses:

1. After 10 to 14 days of wear, the distance, binocular, high luminance, high contrast visual acuity score for the Test lens will be statistically better than +0.01 logMAR.
2. After 10 to 14 days of wear, the intermediate, binocular, high luminance, high contrast visual acuity score for the Test lens will be statistically better than +0.17 logMAR.
3. After 10 to 14 days of wear, the near, binocular, high luminance, high contrast visual acuity score for the Test lens will be statistically better than +0.17 logMAR.
4. After the first 10 to 14 days of wear, the PRO CLUE vision scores for the Test lens will be statistically better than 32 CLUE points. This will be recorded by the subject using the CLUE Follow-up Questionnaire from Visit 2.

If all the primary hypotheses are met, the following secondary hypotheses will be tested.

Secondary Hypotheses:

The PRO CLUE vision scores after the second 10 to 14 days wear cycle (Visit 4) will be statistically better than the score after the first 10 to 14 days wear cycle (Visit 2). This will be recorded using the CLUE Follow-up Questionnaire.

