14.2. Sample Size Justification

A total of 80 subjects (48 myopes and 32 hyperopes) are targeted to complete the study.

Using the POWER procedure in SAS 9.4, below is the summary of sample size required based on the different assumptions of the true LogMAR visual acuity and CLUE scores. The sample size was calculated for the non-inferiority tests (using 0.05 as the margin) with at least 90% of statistical power and 2-sided type I error of 0.05. Assuming the true LogMAR visual acuity is between 0.00 to 0.05 (distance) or 0.08 to 0.12 (near), and true CLUE vision score is between 38 to 42 points.

- Binocular LogMAR visual acuity (distance)

True Value	Estimated Standard Deviation	# of subjects needed	Actual Power
0.00	0.12	18	0.915
0.02	0.12	26	0.904
0.05	0.12	63	0.902

- Binocular LogMAR visual acuity (intermediate and near)

True Value	Estimated Standard Deviation	# of subjects needed	Actual Power
0.08	0.12	21	0.905
0.10	0.12	33	0.901
0.12	0.12	63	0.902

- CLUE vision score

True Value	Estimated Standard Deviation	# of subjects needed	Actual Power
38	17	87	0.902
40	17	50	0.903
42	17	33	0.906

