Comparisons will be carried out using 95% confidence intervals constructed of least-square means (LSM) from the linear mixed models of CLUE vision scores at the end of first wearing cycle (2 week). Statistically superiority will be concluded if the lower limit of the confidence intervals of the test lens are greater than 32 points.

Secondary Hypothesis:

Comparisons between the wearing cycles (2 week vs 4 week) will be carried out using 95% confidence intervals constructed of least-square means (LSM) differences (4 week – 2 week) from the linear mixed model. The superiority will be established if the lower confidence limit is above 0.

In all models, the Kenward and Roger method⁷ will be used for the calculation of the denominator of degrees of freedom.

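### Section 14.4 promises an overall 5% error rate, but no rule says whether the four primary hypotheses are claimed together or singly; claimed singly, the false-claim risk is up to 9.6%

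*Combined protocol and SAP*

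**What the plan says.** - **Error rate (protocol 14.4).** "All planned analysis for this study will be conducted with an overall type I error rate of 5" per cent. No multiplicity procedure or allocation of alpha follows.
- **Hypotheses (2.3).** Four are primary: distance, intermediate and near binocular acuity, and the CLUE vision score at Visit 2. The only link among them is the step to the secondary hypothesis: "If all the primary hypotheses are met, the following secondary hypotheses will be tested".
- **Decision rules (14.5).** Acuity and CLUE are analysed in separate mixed models. Acuity is superior if the upper 95% limit is below +0.10 logMAR for distance and below +0.17 for intermediate and near. For CLUE: "Statistically superiority will be concluded if the lower limit of the confidence intervals of the test lens are greater than 32 points". No interval is adjusted.
- **Sample size (14.2).** "A total of 80 subjects (48 myopes and 32 hyperopes) are targeted to complete the study". Each endpoint has its own table, sized "with at least 90% of statistical power and 2-sided type I error of 0.05". The assumed true means run from 0.00 up to 0.05 logMAR for distance, from 0.08 up to 0.12 for intermediate and near, and from 38 up to 42 for CLUE. No joint power is reported.

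**The concern.** An overall error rate is a property of the whole set of claims, so it depends on how the four conclusions combine. The plan does not say. It could mean one claim that needs all four, which is error-controlled without adjustment. It could equally mean four claims that each stand on their own interval, as 14.5 is worded, and then the 5% in 14.4 is not delivered.

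This matters for a split result. If acuity succeeds and CLUE fails, nothing in the plan prevents reporting the acuity results as confirmed primary findings, and the reading could be chosen after the data are known. Under the all-four reading, the probability of meeting the primary objective and reaching the secondary test is a joint one, and 14.2 does not show it.

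**Working it through.** **Inputs.** Thresholds +0.10, +0.17 and 32 (14.5); SD 0.12 logMAR and 17 CLUE points, true values, and n = 80 (14.2); two-sided 5%, that is 0.025 in the direction of the claim. Correlations between endpoints are not in the documents, so they are assumed and shown as ranges, written as acuity-acuity / acuity-CLUE. A one-sample t-test stands in for the mixed models, and all 80 completers are taken to be in the per-protocol set.

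**1. The plan's own figures.** Power = P(T > t(0.975, n-1)), where T is noncentral t with n-1 degrees of freedom and noncentrality |true value - threshold| × √n / SD.
- Distance row "0.05 0.12 63 0.902": 0.05 × √63 / 0.12 = 3.31, power 0.902.
- CLUE 38 at n = 87: 6 × √87 / 17 = 3.29, power 0.902.

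All nine sample sizes reproduce exactly and all nine powers to three decimals. They are therefore correct powers for one test each.

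**2. Error rate if claims stand singly.** With k true nulls, each at threshold, and independence, P(at least one false claim) = 1 - (1 - 0.025)^k:
- k = 2: 4.9%
- k = 3: 7.3%
- k = 4: 1 - 0.975^4 = 9.6% (bound for any dependence: 4 × 2.5% = 10%)

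Simulated with k = 4: 8.7% (0.3/0.1), 8.2% (0.5/0.3), 6.9% (0.8/0.3), 6.5% (0.8/0.6). All exceed 5%.

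**3. Error rate if all four are required.** A false overall claim needs at least one true null to be rejected along with the rest, so its probability is at most 2.5%.

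**4. Power of each test at n = 80.**
- Acuity, least favourable (0.05 distance; 0.12 intermediate or near): 0.05 × √80 / 0.12 = 3.73, power 95.7%
- Acuity, middle: distance 0.02, over 99.9%; intermediate or near 0.10, 99.9%
- CLUE 38: 6 × √80 / 17 = 3.16, power 87.7%
- CLUE 40: 98.6%; CLUE 42: 99.9%

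**5. Joint power at n = 80.**

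| Distance; intermediate and near; CLUE | Independence | Assumed positive correlations | Bounds |
|---|---|---|---|
| 0.00; 0.08; 42 | 99.9% | – | – |
| 0.02; 0.10; 40 | 98.5% | – | 98.5% to 98.6% |
| 0.05; 0.12; 40 | 0.957³ × 0.986 = 86.5% | about 89% (0.5/0.3), about 90% (0.7/0.3), 91.4% (0.8/0.6) | 85.8% to 95.7% |
| 0.05; 0.12; 38 | 0.957³ × 0.877 = 76.9% | 78.2% (0.3/0.1), 79.8% (0.5/0.3), 83.8% (0.8/0.6) | 74.9% to 87.7% |

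The lower bound is 1 minus the sum of the four single-test failure probabilities. The upper bound is the smallest single-test power. With CLUE at 38 and the acuities at their favourable or middle values, joint power is 87.7% or 87.5%. That shortfall is almost entirely the CLUE test alone, for which 14.2 asks for 87 subjects.

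**The case against.** **The all-four reading is the natural one.** An overall 5% in 14.4 together with the gate in 2.3 fits a single objective that needs all four hypotheses, and then no adjustment is required. No sentence says that one endpoint alone counts as study success, and this is a single-arm Phase 2 evaluation. This stands as a reason to expect that the sponsor means all four. It does not replace the rule: 2.3 conditions only the secondary test, and 14.5 concludes by endpoint.

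**The 9.6% is a worst case.** It needs all four true values at their thresholds and independence. Under independence, two true nulls give 4.9%, just inside 5%. This also stands, but error control must hold whichever nulls are true, and every four-null scenario computed exceeds 5%.

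**A stronger reading on power is not supported.** A reader might infer that if all four are required, the stated 90% power is wrong. Section 14.2 makes no joint claim, its rows are correct as per-test powers, and joint power is well above 90% at the middle and favourable rows.

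A reader might also infer that tests which each exceed 90% at 80 subjects must miss 90% jointly. Treating intermediate and near separately, there are 54 combinations of the tabulated true values with CLUE at 40 or 42. Under independence 52 of them stay above 90% (lowest 90.3%). The two that miss have all three acuities at their least favourable values, and even there about 90% or more is reached once the acuity correlation is about 0.7. The acuities come from the same subjects at the same visit and 14.5 models their covariance, so substantial correlation is plausible, though the documents give no value.

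**Conclusion.** The concern holds for the error rate. As written, 14.5 allows four separate conclusions whose combined false-claim probability is up to 9.6% under independence, or about 6-9% under the assumed positive correlations, against the 5% in 14.4. Under an all-four rule it is at most 2.5%.

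On power the defect is an omission and not a wrong figure. Joint power at 80 falls below 90% only toward the unfavourable end of the assumed ranges, and the 77-84% with CLUE at 38 partly reflects the separate single-test shortfall of 80 against 87 subjects. It would therefore be wrong to put that figure in place of the 90% as if multiplicity alone produced it.

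The figures rest on the assumptions listed with the inputs. They also use +0.10 for distance, the threshold in 14.5 that reproduces the table. Section 2.3 gives +0.01 for the same hypothesis, and the two must be reconciled separately.

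**What to change.** - **14.4:** state that the primary objective is met only if all four primary hypotheses are met, each at two-sided 5%, and that none is claimed as confirmatory otherwise. No alpha adjustment is then needed.
- **If separate claims are wanted:** name Holm over the four. At its strictest step (two-sided 0.0125) power at 80 in the least favourable rows is 87.6% for each acuity test and 72.5% for CLUE. Holm does at least this well.
- **14.2:** label the tabulated powers as per hypothesis. Add joint power at 80 with its assumptions: above 99% (favourable rows), about 98% (middle rows), about 87-91% (all acuities least favourable, CLUE 40), and about 77-84% with bounds 75-88% (the same acuities, CLUE 38), noting that the table asks for 87 subjects in that CLUE row.

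**Cost:** wording only under the all-four rule, with no extra subjects. The reported power looks less favourable at the low end, and a split result can no longer be presented as confirmatory.
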